**Does early higher intravenous lipid intake decrease weight loss in very low birth weight infants?
(REB-17-2236)**

Primary Investigator: [name] MSc

Co-Investigators:

[name], Neonatal–Perinatal Fellow

[name] PhD

[name] FAAP

[name], RD

[name], RD

[name], Research Coordinator

[name], Research Assistant

Dec 27, 2017

Background:

The recommendation of the Pediatric Societies of North America and Europe is that postnatal growth of preterm infants matches the in-utero growth rates of fetuses that remain in utero until full-term.¹⁻³ Despite this long standing recommendation, approximately 43% to 97% of very low birth weight (VLBW, less than 1500 g) infants grow slower than the estimated fetal growth velocity.^{4,5} This slow postnatal growth usually results in extra-uterine growth restriction (EUGR), defined as having a measured growth parameter (weight, length, or head circumference) that is less than 10th percentile of intrauterine growth expectation based on estimated postmenstrual age (PMA) in premature neonates at the time of hospital discharge.⁴ EUGR is associated with major morbidities such as bronchopulmonary dysplasia (BPD), retinopathy of prematurity (ROP) and impaired neurodevelopment.^{4,6-8}

Although the etiology of EUGR is multifactorial, inadequate nutrition plays a pivotal role.^{5,9} There are three critical stages of nutrition support in VLBW infants: (1) acute stage during the first 1-3 weeks after birth when infants are on parenteral nutrition, (2) intermediate period when infants are slowly advanced to full enteral nutrition (growing care stage), and (3) the post-discharge stage.¹⁰ Failure to provide adequate nutrition in the acute stage result in cumulative energy and protein deficits that is difficult to reverse in the second stage. Inadequate early postnatal nutrition results in excessive weight loss that cannot be explained by the physiologic contraction of body water alone. The regain of birth weight may need two to three weeks or even longer in preterm infants with excessive postnatal weight loss.¹¹

Newborn infants born at term normally lose 5-10% of their body weight in the first week of life due to contraction of extracellular water compartment.^{12,13} The proportion of weight loss is significantly higher in VLBW infants.¹² Increased insensible water loss is widely considered as the main cause for additional weight loss in this population.^{14,15} Nevertheless, studies identified low energy intake to be a key driver to excessive weight loss.^{13,16} In fact, an earlier study showed that significant postnatal weight loss occurs mainly in infants whose energy intake is inadequate.¹³ A more recent epidemiologic study demonstrated similar postnatal growth trajectories with minimal crossing of percentiles after the initial weight loss regardless of gestational age at birth.¹¹ The growth trajectories for infants in that study had similar slopes and growth rates which indicate that proportion of postnatal weight loss is a lead cause for EUGR at discharge.¹¹ Therefore, we speculate that decreasing the maximum percentage of initial weight loss in the acute stage would keep the preterm infant on a higher growth trajectory that is enough to reduce incidence of EUGR.

Current fat provision regimen for preterm infants include starting parenteral lipid at 12-24 hours of age with 0.5-1 g/kg per day and advancing by 0.5 g/kg/day until reaching 3 g/kg per day. Using early (within one hour of birth) and higher (start at 2 g/kg per day and advance to 3g/kg per day once total fluid intake is increased to 80 ml/kg/day) parenteral fat intake could reduce the cumulative caloric deficit in the acute stage. Because of high-density energy in fat, higher parenteral fat intake will reduce the early energy deficit and enhance protein accretion. The first 2-3 weeks of life offer a critical window to limit postnatal nutritional and energy deficits.⁵ Recent study showed that higher energy and fat intakes during the first 2 weeks after birth are associated with a lower incidence of brain lesions and dysmaturation at term equivalent age in preterm neonates.¹⁷

To date, studies of “early aggressive nutrition” in preterm infants have mainly focused on high protein intake to prevent protein catabolism.¹⁸⁻²¹ Nevertheless, provision of high protein intake without enough energy is unlikely to significantly reduce the early loss of protein and fat mass that had been accreted before birth. Early and high protein intake is currently a standard of care in our neonatal intensive care unit (NICU).

In summary, provision of high and early fat intake may help reducing the amount of postnatal weight loss. It may also help utilize the high amount of protein that is currently recommended to these premature babies. Also, we expect babies who get this appropriate intake to regain their birth weight earlier than others on slow fat increase regimen.

Methodology

Hypothesis:

We hypothesize that early higher fat intake in the first week after birth in VLBW infants results in less weight loss compared to the traditional provision of intravenous fat.

Study Design:

This is a randomized, non-blinded, controlled trial that will take place from March 2018 through February 2020 at the 39-bed level III NICU at Foothills Medical Center, Calgary, Alberta.

Intervention:

Starting Intravenous Lipid emulsions from D0 at 2 g/kg/day in the experimental group and increase to 3 g/kg/day the next day.

Comparison:

Control group: traditional start by 0.5-1 g/kg/day on D0 and increase daily by 0.5 g/kg/day till reaching 3 g/kg/day.

Outcome:

- Primary: The maximum percentage of weight loss in the acute stage of nutritional support: Defined as (birth weight–lowest postnatal weight)/birth weight× 100).
- Secondary:
 - Time to regain birth weight (day).
 - Time to reach 90 Kcal/kg/day (day).
 - Lipid tolerance: using serum TG levels (intolerance will be defined as TG> 2.8 mmol/L).
 - Incidence of EUGR at 36 weeks and at discharge.
 - Growth anthropometrics (weight, length and HC Z scores at 36 weeks and at discharge).
 - Incidence of ROP, BPD (28 days, 36 weeks CGA), brain injury and NEC.
 - Survival free major morbidity (BPD, ROP, NEC and severe IVH) at discharge.
 - Incidence of severe neurodevelopmental outcome at 18-22 months corrected gestation.
 - Length of stay.
 - Death.

Study Population:

a) Inclusion Criteria:

1. Preterm infants born with birth weight < 1500 g at Foothills Medical Centre (FMC)
2. Appropriate for gestational age (AGA) as per Fenton's growth charts
3. Anticipated duration of PN for >7 days

b) Exclusion Criteria:

1. Infants with congenital anomalies
2. Infants with suspected inborn errors of metabolism or family history of inborn error of metabolism
3. Infants with suspected or confirmed biliary atresia
4. Infants born small for gestational age (SGA)
5. Confirmed early sepsis

Twins and triplets who meet the weight and AGA status criteria will be randomized to the same arm of the study. Informed written consent will be obtained from a parent of each infant before birth or shortly after the infant's admission to the NICU and before starting parenteral lipid emulsions.

Time frame: March, 2018 to April, 2020

Study Protocol:

The investigators will conduct the randomization using a computer-generated allocation sequence (in random sized blocks for allocation concealment and balanced groups) generated at the University of Calgary. The lipid emulsions will be administered through an umbilical venous catheter, peripherally inserted central catheter, or peripheral line. The control group will begin treatment with 0.5 g/kg per day of 20% Intravenous Lipid Emulsion (IVLE) after birth if the birth weight is less or equal 1000g or 1 g/kg per day if birth weight is more than 1000g. The experimental group will begin treatment with 2 g/kg per day of 20% IVLE after birth. The IVLE dose in the control group will be increased by 0.5 g/kg per day daily until reaching 3 g/kg per day. The dose of IVLE will be increased directly from 2 to 3 g/kg per day the next day in the experimental group. Other macronutrients and micronutrients will be provided using the same products for amino acid and dextrose solutions in both groups. The maximum intake of amino acid will be 4 g/kg per day. The initial dextrose concentration in the parenteral nutrition (PN) will be 12.5%. The glucose infusion rate will be calculated and will be adjusted at the discretion of the attending neonatologist depending on the blood sugar levels. Total fluid intake will be started at 60 mL/kg per day for all infants. Monitoring for serum triglyceride will be performed after 24h of each lipid increment as per NICU policy in VLBW infants. This is part of routine care and not additional investigation. The serum triglyceride (TG) levels and other biochemical measurements such as serum electrolytes and acid-base status will be analyzed by the Calgary laboratory services at FMC. If hypertriglyceridemia occurs (>2.8 mmol/L, as per our current protocol), the IVLE concentration will be adjusted according to the following approved algorithm (Table 1).

Triglyceride Level (mmol/L)	Action
< 2.8	
 • Advance lipid intake as planned
2.8 – 4.5	
 • Reduce to previously tolerated dose
Greater than 4.5	
 • Stop lipid infusion for 24 hours

Table 1: Algorithm for adjusting IVLE in TPN.

Infants will be weighed every day on electronic scales with a precision of 2 grams by nursing personnel, using the In-Bed scale. Other anthropometric measurements such as length and head circumference will be taken by nursing personnel on admission and then weekly till discharge with a newborn length board and measuring tape respectively. Classification of newborns to define appropriate-for gestational age (AGA) status for infants at admission to the NICU will be based on Fenton’s Growth Curves. Humidity in the incubators to minimize insensible water loss will be used as per our thermoregulation protocol for preterm and VLBW infants.

Data Collection and Outcome Variables:

Data collection will be completed by research assistant employed in the NICU. After the infants are enrolled, the neonatal-perinatal fellow or research assistant will collect the following information: maternal and neonatal demographic data, birth weight, gestational age at birth, daily weight, serum triglyceride levels, and other nutritional laboratory values during the days on PN, dose of IVLE, fluid intake, maximum percentage of weight loss (defined as: (birth weight–lowest postnatal weight)/birth weight× 100), and day of regaining birth weight. To determine the day of regaining birth weight, the infant should have 2 consecutive readings above the birth weight, then the first day of the 2 readings will be considered the day of regaining birth weight. The study team will collect clinical outcomes such as necrotizing enterocolitis (NEC) (Stage II and above according to Bell staging), BPD, intraventricular hemorrhage (IVH), ROP, death and EUGR. Survival free major morbidity (BPD, severe ROP, NEC and severe IVH) at discharge will be collected and analyzed. Data on neurodevelopmental outcome by 18-22 months corrected gestation for baby less than 29 weeks will be collected from the neonatal follow-up clinic. BPD will be defined as being dependent on oxygen at postmenstrual age of 36 weeks. Intraventricular hemorrhage will be defined based on ultrasound scans obtained before day 15 of life according to the classification of Volpe and Levene. EUGR will be defined for our study

as the presence of a measured weight below the 10th percentile at the time of hospital discharge on Fenton's growth Charts. Hyperglycemia will be defined as glucose level >10 mmol/L. Two registered dietitians will calculate fluids, calories and protein intakes and record the day of life when the infants achieved 100 and 120 ml/kg per day and age when PICC line is removed.

Sample Size and Statistical Analyses:

The primary statistical analysis will be to determine the effect of higher rates of parenteral fat intake on the maximum percentage of postnatal weight loss of the VLBW infants, during the first week of life. Independent, 2-sample, *t* tests will be used to compare the two groups for this primary outcome. Our previous data showed a maximum percent of weight loss in VLBW infants of: 11.4 (SD= 5.2). Drenckpohl et al. found that the weight loss in the first week was 8% only in the experimental group of VLBW infants who received higher dose of IVLE.²² We considered 8% a reasonable percentage of weight loss in this category of infants and calculated our sample size to decrease our percentage by 3.4% (from 11.4% to 8%). Assuming an α value of 0.05 and a power of 0.80, a sample size of 76 infants (38 in each group) will be required.

Continuous variables such as days to achieve 90 kcal/kg per day, biochemical laboratory results, amount of lipid infused, and anthropometric results will be analyzed using independent, 2-sample *t* tests. Categorical variables such as hypertriglyceridemia, proportions of EUGR infants, IVH, BPD and ROP will be evaluated using Pearson χ^2 tests. All statistical tests will be 2-tailed, and the level of significance will be set at 0.05. All statistical analyses will be performed using STATA 11.1 (College Station, TX).

Feasibility and safety:

There are currently about 225 infants born at less than 1500 grams at FMC every year. With a 30% enrollment rate, the sample size will be reached in around 18 months. Halfway through enrollment, the overall rate of lipid intolerance will be reviewed. This will allow for a check for any unexplained sudden increase in incidence of lipid intolerance in relation to the study, or a significant reduction that may allow decreasing of the number needed to enroll. Neonatology section research assistant and study coordinator will help in recruiting and collecting the data.

Plans for dissemination or translation of results and plans for next steps in study of topic:

Findings from this study will generate insight into the effects and tolerance of high and early parenteral fat use in preterm infants. It will further provide answers whether the experimental regimen provides normal level of TG. The study will also set the basis to test the long term neurodevelopmental outcome for infants who received the new regimen of fat in the near future. If the results of the study indicate clinical benefit, this would provide evidence for generalizing the use of the new regimen routinely in the NICU.

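### Eligible twins and triplets are allocated together to one arm, but the tests and the 76-infant sample size treat every infant as independent, so the 5% level is not protected if complete sibling sets enrol with positively correlated outcomes.

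*Combined protocol and SAP*

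**What the plan says.** On allocation, the paragraph after the Exclusion Criteria (Study Population) says: "Twins and triplets who meet the weight and AGA status criteria will be randomized to the same arm of the study". The Study Protocol section adds only that there is a "computer-generated allocation sequence (in random sized blocks for allocation concealment and balanced groups". It does not say how a sibling set enters the sequence.

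On analysis, the Sample Size and Statistical Analyses section names independent two-sample t "tests will be used to compare the two groups for this primary outcome". For continuous secondary outcomes, "anthropometric results will be analyzed using independent, 2-sample" t tests. For binary outcomes, "Categorical variables such as hypertriglyceridemia, proportions of EUGR infants, IVH, BPD and ROP will be evaluated using Pearson" chi-square tests. For the level, "All statistical tests will be 2-tailed, and the level of significance will be set at 0.05".

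On size: "Assuming an α value of 0.05 and a power of 0.80, a sample size of 76 infants (38 in each group) will be required". The inputs are a mean maximum weight loss of 11.4% (SD 5.2) and a target of 8%.

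No section mentions a design effect, a within-set correlation, a mixed model, generalised estimating equations, a cluster-robust variance, or the selection of one infant per set.

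**The concern.** For multiples, the unit that is randomised is the sibling set, while the unit that is analysed is the infant. Siblings share a mother, a pregnancy and a gestational age, so a positive correlation in early weight loss is plausible, though the documents give no evidence of it. When siblings sit in the same arm, any positive correlation adds to the variance of the difference between arms. The independent-samples t test leaves that part out.

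Two stated quantities are then at stake. The first is the 0.05 level, which the primary test would not hold. The second is the power of 0.80, which was calculated for 76 independent infants and does not describe a valid sibling-aware analysis of the same 76.

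**Working it through.** **1. The plan's own figure.** Inputs from Sample Size and Statistical Analyses: difference 11.4 − 8 = 3.4, SD 5.2, two-sided alpha 0.05, power 0.80.

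- Normal approximation: n per group = 2 × (1.960 + 0.842)² × (5.2/3.4)² = 36.7, so 37.
- Noncentral t: 37.7 per group, so 38. Power is 0.792 at 37 and 0.803 at 38.

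The stated 76 is therefore reproduced exactly as the number for independent infants. It contains no allowance for siblings.

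**2. Variance with same-arm twin pairs.** Take n infants per arm, of whom 2k are in complete pairs, with within-pair correlation ICC. Then

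Var(arm mean) = (SD²/n) × [1 + (2k/n) × ICC].

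The design effect is DE = 1 + share × ICC, where share = 2k/n. A set with only one eligible sibling counts as a singleton.

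**3. Type I error of the planned t test.** The true standard error is larger than the one the test uses by about √DE, so

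type I error ≈ 2 × P(T with 74 df > 1.9925/√DE).

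Share and ICC are both assumed. With 2, 4 or 6 pairs per arm of 38, the share is 4/38 = 10.5%, 8/38 = 21% or 12/38 = 32%. Each cell gives the formula, then a simulation of the planned test (38 per arm, 100,000 runs).

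| Share in pairs | ICC 0.1 | ICC 0.3 | ICC 0.5 | ICC 0.7 |
|---|---|---|---|---|
| 10.5% | 0.051; 0.053 | 0.054; 0.054 | 0.056; 0.056 | 0.058; 0.058 |
| 21% | 0.052; 0.053 | 0.057; 0.057 | 0.062; 0.061 | 0.067; 0.067 |
| 32% | 0.054; 0.054 | 0.061; 0.060 | 0.068; 0.069 | 0.075; 0.077 |

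Simulation error is about ±0.0014, and separate simulations agree to within about 0.002. The lowest case cannot be told apart from 0.05. The error passes 0.06 only when share × ICC exceeds about 0.086.

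**4. Middle case in full.** Share 0.21 and ICC 0.3 give DE = 1 + 0.21 × 0.3 = 1.063 and √DE = 1.031. The standard error is about 3% too small. The critical ratio falls to 1.9925/1.031 = 1.933, and the type I error is about 0.057.

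**5. Power.** The planned t test still rejects in about 0.78 to 0.80 of simulated trials under the 3.4-point effect. A valid analysis of 76 infants has less. By normal approximation, power = Φ(2.850/√DE − 1.960), where 2.850 = 3.4/(5.2 × √(2/38)).

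- No siblings: Φ(0.890) = 0.813.
- DE 1.063: Φ(0.804) = 0.789.
- DE 1.221 (32%, ICC 0.7): Φ(0.619) = 0.732.

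Simulating a REML mixed model with a random intercept per mother and (mothers − 2) df gives about 0.80 at 10.5% and ICC 0.1, 0.78 in the middle case, and 0.74 at the top of the range. Its type I error stays within about 0.003 of 0.05. If siblings are in fact uncorrelated, its power is 0.79 to 0.80, against 0.803 for the t test.

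**The case against.** The strongest reply is that the consequence rests wholly on assumed inputs. Each sibling must separately be under 1500 g, appropriate for gestational age, expected to need parenteral nutrition for more than 7 days, and free of the exclusions. The share of infants in complete sets may therefore be well below the share of multiples born. In the middle case the error is 0.057 rather than 0.05, which is small for a single-centre trial. This stands, and it is why the point is put as conditional and modest. It does not remove the mismatch: the plan foresees sibling sets and names a test that is valid only if none enrol complete or their outcomes are uncorrelated.

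For binary outcomes the gain is small. At an assumed 30% event rate the Pearson test has a type I error of 0.052 to 0.053 with no sibling correlation and 0.058 in the middle case. One sentence in the plan is enough there.

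With few pairs the between-mother variance is poorly estimated. In the middle case REML puts it at zero in about 20% of simulated trials, and the analysis then matches the planned t test. That is true, but the error rates given for the mixed model include those trials. Other cluster methods with a small-sample correction would also serve.

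A reader might infer more: that same-arm allocation is itself the error, that the treatment estimate is biased, or that the planned t test loses its power. The documents support none of these. Same-arm allocation is a legitimate design, correlation changes the standard error rather than the expected difference, and the planned test's rejection rate barely moves.

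**Conclusion.** The point holds in conditional form and should be fixed. That allocation by sibling set is followed by analysis by infant is certain from the text, and nothing elsewhere in the plan repairs it. That the primary test exceeds 5% depends on two conditions the documents do not settle: complete sets enrol, and sibling outcomes are positively correlated. Over the assumed twin-pair range the type I error is about 0.05 to 0.077, about 0.055 to 0.057 at 21% and ICC 0.3, and possibly indistinguishable from 0.05 at low values.

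It would be wrong to conclude that the trial will have a materially inflated error rate. The upper figure belongs to one corner of an assumed grid, and same-arm allocation is not evidence that the correlation exists. Nor does it follow that 76 infants are too few. What follows is that the unqualified 0.80 does not describe a valid analysis.

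**What to change.** Keep same-arm allocation and record a mother identifier. The Data Collection section already gathers "maternal and neonatal demographic data, birth weight, gestational age at birth, daily weight", so this adds one field.

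Prespecify one sibling-aware primary analysis with a small-sample correction. An example is a linear mixed model fitted by REML, with a random intercept per mother, tested on (mothers − 2) degrees of freedom. State that the planned t test is used if no complete set enrols or if the variance component cannot be estimated.

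Add one sentence that continuous and binary secondary outcomes will also be analysed allowing for sibling sets, for example with cluster-robust errors by mother and a small-sample correction.

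Replace the unqualified 0.80 with the power of 76 infants under this analysis, for a declared multiple-birth share and ICC and a range that includes low values. Over the values assumed here it runs from about 0.80 down to about 0.74. Holding the sample at 76 and disclosing that range is a judgement; no extra enrolment is needed to make the analysis valid.

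The cost is a rewrite of a few sentences, a slightly larger standard error (about 3% in the middle case), and about 0.01 of power if siblings turn out to be uncorrelated.

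### TG tests are tied to lipid increments, so the arms have unequal chances of a value above 2.8 mmol/L being found; the hypertriglyceridemia comparison can lean towards the experimental regimen, by an unknown amount

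*Combined protocol and SAP*

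**What the plan says.** All references are to the combined protocol and SAP.

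- **Sampling (Study Protocol):** "Monitoring for serum triglyceride will be performed after 24h of each lipid increment as per NICU policy in VLBW infants". The protocol describes this as routine care. No other TG schedule is given, and the unit policy itself is not reproduced.
- **Dose steps (Study Protocol, Appendix):** for control, "The IVLE dose in the control group will be increased by 0.5 g/kg per day daily until reaching 3 g/kg per day", starting from 0.5 g/kg/day (1000 g or less) or 1 g/kg/day (above 1000 g). For the experimental arm, "The dose of IVLE will be increased directly from 2 to 3 g/kg per day the next day in the experimental group".
- **Table 1:** a TG below 2.8 mmol/L leads to "Advance lipid intake as planned". Advancing therefore depends on a TG result.
- **Outcome (Secondary):** "Lipid tolerance: using serum TG levels (intolerance will be defined as TG> 2.8 mmol/L". No window, dose level or number of tests is attached.
- **Data Collection and Outcome Variables:** the study collects "serum triglyceride levels, and other nutritional laboratory values during the days on PN", with no fixed sampling days.
- **Sample Size and Statistical Analyses:** "Categorical variables such as hypertriglyceridemia, proportions of EUGR infants, IVH, BPD and ROP will be evaluated using Pearson" chi-square tests. Two-sample t tests are planned for "Continuous variables such as days to achieve 90 kcal/kg per day, biochemical laboratory results" and other measures, with no time point named for the laboratory values.

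**The concern.** The trial randomises how fast lipid is advanced, and the stated sampling rule follows each advance. The experimental regimen reaches 3 g/kg/day in one step and the control regimen in four or five. The rule is the same in both arms but yields fewer scheduled tests in the experimental arm. That arm also has no stated test after about Day 2, although it is planned at 3 g/kg/day from Day 1.

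If an infant counts as intolerant when any TG exceeds 2.8, the arm tested more often has more chances to be counted. A tie, or a lower rate in the experimental arm, could then come partly from less testing. This matters because TG is the protocol's named measure of lipid tolerance. The dissemination section also says the trial will show whether the experimental regimen gives normal TG levels, and it envisages routine use if benefit is found.

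**Working it through.** **The plan's own figures.** The documents give no TG rate, test count or TG sample size. The figure used below is 38 per arm. It reproduces: for a difference of 3.4, SD 5.2, two-sided 0.05 and power 0.80, the t-based solution is 37.7, hence 38 per arm and 76 in total.

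**Scheduled tests (daily rows of the Appendix, Days 0-5).**

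| | Doses, g/kg/day | Increments | With starting dose | Planned days at 3 g/kg/day |
|---|---|---|---|---|
| Experimental | 2, 3, 3, 3, 3, 3 | 1 | 2 | 5 |
| Control, 1000 g or less | 0.5, 1, 1.5, 2, 2.5, 3 | 5 | 6 | 1 |
| Control, above 1000 g | 1, 1.5, 2, 2.5, 3, 3 | 4 | 5 | 2 |

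At 38 per arm, with the starting dose sampled, this is 38 × 2 = 76 tests against 38 × 5 = 190 to 38 × 6 = 228. Without it, it is 38 against 152 to 190. Each group has exactly one scheduled test at 3 g/kg/day.

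**Chance of any TG above 2.8.** The per-test risk and the within-infant correlation are not in the documents, so both are assumed. Let p_d be the risk at dose d, the same in both arms, with p = 5% at 3 g/kg/day. Four shapes are used:
- only at 3 g/kg/day;
- proportional, p_d = p × d/3;
- zero below 2 g/kg/day and p from there up;
- flat, p_d = p.

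Independent tests: P(any) = 1 − ∏(1 − p_d). Correlated tests: P(any) = 1 − ∫ φ(u) ∏ Φ((t_d − √ρ·u)/√(1 − ρ)) du, with t_d = Φ⁻¹(1 − p_d) and ρ = 0.8. Only the first exceedance counts, so dose changes made after it do not alter these figures.

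Results at ρ = 0.8 with the starting dose sampled, experimental vs control (ranges cover the two weight strata):

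| Risk shape | As scheduled | Equal daily testing, Days 0-5 |
|---|---|---|
| Only at 3 | 5.0% vs 5.0% | 11.7% vs 5.0-7.5% |
| Proportional | 6.4% vs 8.6% | 12.1% vs 8.6-10.0% |
| Zero below 2 | 7.5% vs 9.3% | 12.6% vs 9.3-10.6% |
| Flat | 7.5% vs 11.7-12.6% | 12.6% vs 12.6% |

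There are two ways to read this, and they should be kept apart.
- The raw scheduled difference (control minus experimental) runs from 0 to 12.6 − 7.5 = 5.1 points.
- Against equal daily testing, the proportional case moves from +2.1 (12.1 − 10.0) or +3.5 (12.1 − 8.6) to 6.4 − 8.6 = −2.2. In the only-at-3 case, the 5.0% tie replaces an excess of 4.2 (11.7 − 7.5) to 6.7 (11.7 − 5.0) points.

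**Sensitivity.** Proportional risk, ρ = 0.8, as scheduled:
- p = 2%: 2.7% vs 3.8%;
- p = 10%: 12.3% vs 15.7-15.8%;
- p = 20%: 23.5% vs 28.4%.

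Flat risk with independent tests is the upper extreme at 5%: 1 − 0.95² = 9.8% vs 1 − 0.95⁵ = 22.6% to 1 − 0.95⁶ = 26.5%. With perfect correlation and flat risk there is no lean.

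**The case against.** **The unit policy is not in the documents.** The stated schedule may be only a minimum. TG values are collected throughout parenteral nutrition, which is anticipated to last more than 7 days, and the trial is not blinded. Further samples could narrow, widen or reverse the gap. This stands, and it is why no size can be claimed.

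**Any TG above 2.8 is not the plan's wording.** It supplies a threshold and a test. This also stands: the lean follows from a natural reading, not from stated text.

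**The schedule is balanced at the target dose, with one test per arm.** True. The share of days at 3 g/kg/day that are tested (1 of 5 against 1 of 1 or 1 of 2) also depends on stopping at Day 5. If 3 g/kg/day continued through Day 7, it would be 1 of 7 against 1 of 3 or 1 of 4. The imbalance shrinks but remains.

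**A matched-age analysis brings its own distortion.** At 24 h after the Day 1 increment it sets 3 g/kg/day against 1 or 1.5. Under the zero-below-2 model it gives 7.5% vs 0%. Equal daily testing gives +2.0 (12.6 − 10.6) to +3.3 (12.6 − 9.3), so its error is 4.2 to 5.5 points. The scheduled comparison (7.5 − 9.3 = −1.8) errs by 3.8 to 5.1 in the other direction. This stands and rules it out as the sole lead analysis.

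**Stronger readings that a reader might infer.** One is that the experimental arm is bound to look better tolerated. The only-at-3 model gives equal scheduled rates, so the documents do not support that. Another is that the 9.8% vs 22.6-26.5% contrast is the expected bias. It needs independent tests and the same risk at 0.5 as at 3 g/kg/day, and nothing in the documents supports either.

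**Conclusion.** The concern holds as a minor point. On the stated schedule the number of TG tests depends on assignment: 1 against 4-5, or 2 against 5-6 if the starting dose is sampled. With no window on the outcome, a chi-square on any value above 2.8 can lean towards the experimental regimen. Under the assumed 5% risk and correlation 0.8 the raw scheduled difference is 0 to about 5 points. The true size is unknown and may be nil.

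This rests on three things: the one sampling sentence being the whole schedule, the any-value reading, and assumed risks.

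It would be wrong to infer that the trial's main result is compromised. The primary outcome is weight loss, so its t test and N = 76 do not depend on TG sampling. The half-way review under Feasibility and safety looks at the rate over both arms together and makes no between-arm comparison. Nor do the documents show that TG will be unmeasured after Day 2, only that no test is stated there.

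**What to change.** 1. Report the number and timing of TG tests per infant, by arm.
2. Show any TG above 2.8 over all samples descriptively beside those counts. Do not use its chi-square alone to claim equal or better tolerance.
3. From samples already taken, report two comparisons side by side, with neither as sole lead:
   - *Matched age:* samples up to 24 h after the Day 1 increment, in all randomised infants. An infant not advanced because of an earlier TG above 2.8 counts as above 2.8.
   - *Matched dose:* the first sample at 3 g/kg/day, with the number not reaching that dose by arm.
4. State what each can show. Matched age contrasts 3 with 1-1.5 g/kg/day. Under the same assumptions it gives 7.5% vs 7.5% (flat), 6.4% vs 2.1-3.3% (proportional), 7.5% vs 0% (zero below 2) and 5.0% vs 0% (only at 3). It therefore describes early TG by regimen, not tolerance of the full regimens. Matched dose falls at different ages and is conditional on reaching that dose.
5. State, as a limit on the question of normal TG under the experimental regimen, that its later days at 3 g/kg/day have no stated test unless routine samples exist.

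**Cost:** wording and tables only, with no extra blood samples and no change to N. The comparisons will be imprecise. At an assumed 10% vs 5% with 38 per arm, and treating infants as independent, the 95% CI half-width is 1.96 × √(0.10 × 0.90/38 + 0.05 × 0.95/38) = 11.8 points.
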